1.2 Trial registration

Not prospectively registered (laboratory, minimal-risk, non-therapeutic investigation).

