1.3 Protocol version and date

Version 1.0; 2025-10-03.

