10.4 Subjective scales

TSS (−4...+4; anchors from very cold to very hot), CS (1...5; comfortable to extremely uncomfortable), VAS pain (0–100 mm; no pain to worst pain imaginable). Scripted instructions by the same assessor.

11. Sample Size

An a priori power analysis (G*Power 3.1.9.7) for a two-tailed independent-samples t-test ($\alpha = 0.05$, power = 0.80, anticipated effect size $d = 0.80$) indicated a required sample of 26 participants per group (total $n = 52$). In practice, 39 participants were enrolled and randomised (experimental $n = 20$; control $n = 19$). Of 40 individuals assessed, one was excluded at screening for a health condition. No participants discontinued the intervention or were lost to follow-up. With the achieved sample size, post-hoc power to detect $d = 0.80$ was approximately 0.68; accordingly, findings are interpreted as exploratory/hypothesis-generating.

12. Randomization and Allocation

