12.3. Blinding

Participants and interventionists were not blinded. Thermal image analysis was performed offline by an assessor not involved in data collection. Raw-data preprocessing/curation ([name]) and statistical analyses ([name]) were conducted by team members who did not take part in the experimental procedures and were blinded to group allocation.

13. Statistical Analysis Plan (SAP)

- **Descriptives:** values as mean \pm SD; Table 1 additionally reports min–max where shown.
- **Normality:** Shapiro–Wilk test.
- **Between-group comparisons at prespecified time points:** Student’s t test (normal) or Mann–Whitney U test (non-normal).
- **Within-group pre–post comparisons:** paired Student’s t test (normal) or Wilcoxon signed-rank test (non-normal).
- **Repeated measures:** two-way repeated-measures ANOVA for Tsk (group \times stage; and IRT vs RT within groups), with Bonferroni-adjusted post hoc tests. Effect size: partial η^2 for RM-ANOVA.
- **Significance:** $\alpha = 0.05$; tests two-sided.
- **Analysis set / missing data:** all randomised participants analysed; no imputation (no losses).

14. Data Management and Sharing

De-identified individual participant data (IPD) and the de-identified summary datasets underlying all tables and figures are openly available in Zenodo (DOI: 10.5281/zenodo.17255092) under a CC BY 4.0 license, with no access restrictions or data-use agreement required. The Zenodo record also includes Supplementary File S1 (exact questionnaire wording/anchors) and the full Research Protocol and prespecified Statistical Analysis Plan. De-identified IPD comprise participant-level values for prespecified outcomes and baseline characteristics; direct identifiers, dates, free-text fields, and rare categories were removed or aggregated to minimise re-identification risk. The dataset will be preserved for at least 5 years; enquiries may be directed to the corresponding author.

15. Ethics

Approved by the Bioethics Committee of the Poznań University of Medical Sciences (Resolution No. 360/11). Conducted in accordance with the Declaration of Helsinki. Minimal risk expected.

16. Monitoring and Harms

Adverse events (e.g., excessive pain, skin irritation) monitored throughout; any event recorded with timing, severity, relatedness, and action taken. No interim analyses; trial duration per session ~60–75 minutes.

17. Amendments and Deviations

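### Does calling the SAP prespecified, in a version finalised after data collection, call for a change to the plan?

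*Combined protocol and SAP*

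**What the plan says.** Section 14 uses the word *prespecified* twice. It describes the deposited plan as "the full Research Protocol and prespecified Statistical Analysis Plan" and the shared data as "participant-level values for prespecified outcomes and baseline characteristics". Neither phrase carries a date or a version number.

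The document identifies itself in section 1.3 as "Version 1.0; 2025-10-03", and section 1.2 states "Not prospectively registered". Section 11 gives the target (26 per group, 52 in total) and then the outcome of recruitment: "Of 40 individuals assessed, one was excluded at screening for a health condition", 39 randomised as 20 and 19, and "No participants discontinued the intervention or were lost to follow-up". It adds achieved power of about 0.68 and concludes that the findings are to be read as exploratory. Section 12.2 gives study IDs that end at 039. Section 13 sets no imputation on the ground that there were no losses, and it refers to the content of Table 1. Section 14 says the datasets "underlying all tables and figures are openly available in Zenodo".

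**The concern.** A plan that reports its own final counts cannot, in that version, have been written before the data. The statistical section is affected as well as the sample-size section, because its missing-data rule rests on an observed fact and it describes a table as if finished. With no registration and no earlier version cited, a reader cannot tell from this document when three things were settled: the primary summary (the minimum skin temperature over time points IV to X), the ranking of endpoints, and the full set of tests.

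At stake is the standing of the primary comparison. Someone who trusts the label would read it as an underpowered test of a hypothesis fixed in advance. Someone who doubts it would read it as one of several summaries that might have been chosen once the curves were visible. Section 11 gives low power as its only reason for the exploratory reading, so this second reason for caution is not spelled out.

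**Working it through.** **1. The plan's own figures.** The inputs are all from section 11: two-sided independent-samples t-test, alpha 0.05, d = 0.80. Power comes from the noncentral t distribution with noncentrality λ = d·√(n₁n₂/(n₁+n₂)) and n₁+n₂−2 degrees of freedom.

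- Planned size: solving for power 0.80 gives n = 25.52, so 26 per group and 52 in total, as stated. At 26 per group, λ = 0.80·√(676/52) = 2.88 with 50 degrees of freedom, and power is 0.807.
- Achieved size: λ = 0.80·√(380/39) = 2.50 with 37 degrees of freedom, and power is 0.682, against about 0.68 stated.
- Flow: 40 − 1 = 39 = 20 + 19, which agrees with the IDs in section 12.2.

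The arithmetic is sound. It says nothing about when the plan was fixed; it confirms only the basis on which section 11 calls the findings exploratory.

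**2. Text that dates this version after the data.** Final enrolment, no losses and achieved power (section 11), the last ID (12.2), analyses described as done (12.3), the no-losses rule and Table 1 (13), and posted data (14). Several of these restate the same fact, n = 39, but together they settle the matter.

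**3. Text that points to an earlier plan.**

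- Section 11 describes the power analysis as done a priori and names a two-tailed t-test at alpha 0.05. The document therefore claims that the main test, its sidedness and its level were chosen in advance, although it gives no date and does not name the endpoint.
- A target of 52 that was missed by 52 − 39 = 13 fits a calculation made beforehand, though it does not prove one.
- Section 17 speaks of deviations in the future tense, section 18 of results still to be submitted, and section 8.3 of harms not anticipated.

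This mixture of tenses fits an earlier text later updated with results. It does not date that text.

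**4. What could have been chosen late.** The measured variables, instruments and time points (sections 8 to 10) had to be in place before anyone could be measured. In that sense *prespecified outcomes* in section 14 is defensible, as *prespecified time points* in section 13 is. The analysis set left little to choose, since all 39 randomised were analysed. What remains is the primary summary, the endpoint ranking and the choice of tests.

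**5. What would change if the label were dropped or dated.** The endpoint in 8.1, the tests in section 13, the analysis set and the power would all stay as they are. Section 8.2 already lists skin temperature at each of IV to X as an endpoint, and section 14 releases participant-level values without restriction. A reader can therefore see whether the minimum tells a different story from the rest of the rewarming curve.

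**The case for a change.** The strongest case for a change is that the label makes a claim the document does not support. The ethics resolution is cited by number, with no statement that it covered these endpoints. The a priori wording covers a t-test and not the choice of a minimum over a window. Dates were stripped from the shared data, so the timing cannot be rebuilt from them. Blinded analysis (12.3) and the absence of interim analyses (section 16) do not date a plan, and blinding is weak protection here because the skin temperatures themselves may reveal the arm. The remedy would be cheap: a citation, or the removal of an adjective.

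Most of this stands as description. Prespecification of the primary summary is not shown in this document, and a dated citation would be helpful in the published report. What does not follow is a fault in the plan. The argument shows that a date is missing. It does not show that the label is wrong, because the repository to which section 14 points was not available for this review. No bias is shown, and none can be computed from the documents. The caveat that the remedy would support, an exploratory reading of every finding including the primary one, is already in section 11. A second reason for it would not alter how the results are analysed or how firmly they may be stated.

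**Conclusion.** No change to the plan follows. This version was finalised after data collection and its use of *prespecified* is undated; both are plain on the page. The effect on design, analysis, power and conclusions is nil. Non-registration (1.2), the version date (1.3) and the shortfall from 52 to 39 (section 11) are all disclosed, and the findings are already labelled exploratory. It is a point of documentation: two uses of one word in section 14.

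This rests on two assumptions. The first is that the report keeps section 11's exploratory reading for the primary endpoint as well as the secondary ones. The second is that the rewarming time points in 8.2 are reported in full beside the primary minimum. If the report presented the primary comparison as confirmatory on the strength of the label, the missing date would become material.
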